4.6.6 Post Week 76 Efficacy Analyses

The post-Week 76 efficacy analysis will be performed for the patients who meet the adequate response criteria as assessed by investigator at Week 76 and continue blinded treatment after Week 76. An adequate response is present if all of the following criteria are met (REGENCY, Protocol Section 3.1.2):

- UPCR <0.8 g/g or ≥50% reduction in UPCR from baseline to subnephrotic levels (<3 g/g)
- No deterioration in renal function from baseline (eGFR ≥85% of baseline)
- No need for high-dose corticosteroids
- No receipt of rescue therapy or treatment failure

The primary and the key secondary endpoints will be summarized post-Week 76 at Week 106, 132, 158, 184, and 210, by obinutuzumab and placebo groups for the post Week 76 efficacy analysis. This will enable a supportive, exploratory assessment of maintenance of response, acknowledging the limitations of small sample sizes (particularly at later visits), and potential baseline imbalances between groups.

Proportions by treatment groups will be presented for binary endpoints along with difference in proportions between treatment groups, two-sided 95% CI for the difference.

The estimand attributes for the binary endpoints are defined as follows unless otherwise specified:

- Population: Patients with active or active/chronic ISN/RPS 2003 Class III or IV proliferative LN who meet the adequate response criteria at Week 76.
- Endpoint (variable): The primary and key secondary endpoints at Week 106, 132, 158, 184, and 210
- Treatments:
 - Experimental: Obinutuzumab 1000 mg IV infusion start at Day 1 and Week 2,
 24, 26, and either Weeks 50 and 52 or Week 52 only, Week 80 and every
 6 months thereafter until the study unblinded to investigator and patients
 - Control: Placebo
- Intercurrent events: rescue therapy, treatment failure, study treatment discontinuation, death, early study withdrawal, entering into OLT or entering into SFU prior to endpoint assessment.

Rescue therapy, treatment failure, death, early study withdrawal and entering into the OLT will be handled using a composite strategy.

Study treatment discontinuation will be handled using a treatment policy strategy.

Entering into SFU will be handled using a hypothetical strategy targeting an effect that would occur in the hypothetical scenario in which no patient entered into SFU.

Summary measure: Difference in proportions at a specified visit of interest. The
analysis will only include patients who would reach to the specified visit at the time
of CCOD (patients who moved to OLT or SFU period or withdraw from the study
prior to endpoint assessment, but would otherwise reach to the assessment visit by
CCOD will be included).

Last Observation Carry Forward (LOCF) will be used as the missing data imputation method. Twenty-four-hour UPCR will be imputed in the following order:

- 1. Spot UPCR at the same visit
- 2. 24-hour UPCR at the previous visit
- 3. Spot UPCR at the previous visit

The endpoint proportion of patients who achieve CRR with successful prednisone taper at post-Week 76 weeks will be evaluated as achievement of CRR at the endpoint assessment visit with the following:

 No receipt of prednisone >7.5 mg/day (or equivalent) from 12 week prior to the endpoint assessment visit The endpoint proportion of patients who experience death or renal-related events through the post-Week 76 visits will be evaluated from the beginning of the study.

The change from baseline for eGFR and FACIT-F post Week 76 will be summarized using descriptive statistics. A 95% CI of mean difference between the treatment groups will be presented.

Estimand attributes for the change from baseline for eGFR and FACIT-F are defined as follows:

- Population: Patients with active or active/chronic ISN/RPS 2003 Class III or IV proliferative LN who meet the adequate response criteria at Week 76.
- Endpoint (variable): Change from baseline for eGFR and FACIT-F at Week 106, 132, 158, 184, and 210.
- Treatments:
 - Experimental: Obinutuzumab 1000 mg IV infusion start at Day 1 and Week 2,
 24, 26, and either Weeks 50 and 52 or Week 52 only, Week 80 for every
 6 months until the study unblinded to investigator and patients
 - Control: Placebo
- Intercurrent events: rescue therapy, treatment failure, study treatment discontinuation, death, entering into OLT or entering into SFU prior to endpoint assessment. The treatment policy strategy will be used for all the intercurrent events with the exception of death. Data after death will be imputed with 0.

It is noted that the "Clinically significant, sustained worsening in UPCR and/or eGFR from Week 24 onward that leads the investigator to conclude the patient has failed the randomized treatment regimen" criteria of the treatment failure was not evaluated post Week 76.

Summary measure: Difference in means at a specified visit of interest.

LOCF will be used as missing data imputation method.

The analysis will be based on post Week 76 blinded treatment efficacy-evaluable population as defined below.

Post Week 76 blinded treatment efficacy-evaluable population: Post Week 76 blinded treatment efficacy-evaluable population will consist of patients who continue blinded treatment period post Week 76 and reach at the specified endpoint assessment visits by CCOD. Patients enter the blinded treatment period, but later moved to OLT or SFU period or withdraw from the study prior to endpoint assessment, but would otherwise reach to the assessment visit by CCOD will be included. Patients will be grouped according to randomized (assigned) treatment, rather than treatment received. Patients

who received an incorrect therapy will be reported under the treatment group to which they were randomized.

4.6.7 All Exposure Safety Analyses including Post-Week 76 Data

In addition to the safety analyses detailed in Section 4.5, an All Exposure safety analysis will be performed including post Week 76 data from both blinded treatment and Open-Label Treatment (OLT) period.

The obinutuzumab arm of the All Exposure analysis will comprise of safety data from patients that received any dose of obinutuzumab. Patients that receive any dose of obinutuzumab, whether during the blinded treatment period or post Week 76 via OLT, will contribute safety data from their first dose of obinutuzumab until their last dose +6 months, the CCOD, study withdrawal or receipt of rescue therapy (whichever occurs first):

- Patients randomized to obinutuzumab at Day 1 who achieve adequate or inadequate response at the Week 76 primary analysis will continue to receive obinutuzumab (either blinded or open label). These patients will therefore contribute safety data to the obinutuzumab all exposure arm from their first dose at Day 1 following randomization.
- Patients randomized to placebo at Day 1 who achieve inadequate treatment response at Week 76 will switch to open label obinutuzumab treatment. These patients will therefore contribute safety data to the obinutuzumab all exposure arm following their first dose after switching to obinutuzumab treatment in the OLT period of the trial. Patients that switch from placebo to obinutuzumab will also be rebaselined as of their first dose of obinutuzumab during the OLT period.

The placebo arm of the All Exposure analysis comprises safety data from patients that received any dose of placebo. Patients that received any dose of placebo during the blinded treatment period including post Week 76, will contribute safety data from their first dose of placebo until their last dose+6 months, the CCOD, receipt of obinutuzumab - 1 day or study withdrawal (whichever occurs first):

- Patients randomized to placebo at Day 1 who achieve adequate response at the
 Week 76 primary analysis will continue to receive placebo during continued blinded
 treatment period. These patients will therefore contribute safety data to the placebo
 all exposure arm from their first dose following randomization, until their last placebo
 dose+6 months, the CCOD or study withdrawal (whichever occurs first)
- Patients randomized to placebo at Day 1 who achieve inadequate response at the Week 76 primary analysis will switch to obinutuzumab treatment during OLT period.
 These patients will therefore contribute safety data to the placebo all exposure arm from their first dose following randomization up until they switch to obinutuzumab.

The following will be summarized in the All Exposure safety analysis:

AEs

- SAEs
- AESIs
- Deaths

All exposure safety analysis population: The All exposure safety analysis population is defined as patients who received any part of blinded infusion of obinutuzumab or placebo during blinded treatment or open label treatment period. Patients who were randomized to the study but who did not receive any part of blinded infusion of obinutuzumab or placebo will not be included in the all exposure safety analysis population. Patients will be grouped according to the treatment that patients actually received rather than the treatment assigned.

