The proportion of patients who achieve an ORR, defined as achievement of either CRR or PRR, evaluated at Week 50 will be analyzed using a CMH test with region and race as stratification factors. The definition of CRR is explained in Section 4.2.1. PRR is defined as achievement of all of the following:

- ≥50% reduction in UPCR from baseline
- UPCR <1 (or <3 if the baseline UPCR was ≥3)
- eGFR ≥85% of baseline, as calculated using the CKD-EPI equation
- No occurrence of the following intercurrent events:
 - Rescue therapy, treatment failure, death, or early study withdrawal

Intercurrent events are described in Section 4.2.1.1.

Missing data: Data obtained from the central laboratory only will be used.

Multiple imputations will be used for the missing data imputation using the model specified in Section 4.2.2. The analysis will follow the same methods described in Section 4.2.2.

4.3.1.4 Proportion of Patients who Experience Death or Renal-related Events through Week 76

Proportion of patients who experience death or renal-related events through Week 76, defined as the proportion of patients with one or more of the following events:

- Death
- Treatment failure (see Section 4.2.1.1)
- Worsening proteinuria, defined as a confirmed ≥ 50% increase in UPCR to a value ≥3
- Worsening eGFR, define as a confirmed ≥30% decrease in eGFR to a value <60

Worsening proteinuria and eGFR criteria will be evaluated by calculating the specified increase or decrease from the previous visit.

The death or renal related event will occur if any of the above events occur at any visit through Week 76. The proportion of patients who experience death or renal-related

events through Week 76 will be analyzed using a CMH test with region and race as stratification factors.

Estimand attributes for the endpoint are defined as follows:

- Population: patients with active or active/chronic ISN/RPS 2003 Class III or IV proliferative LN.
- Endpoint (variable): Death or renal-related events as defined above.
- Treatments:

Experimental: Obinutuzumab 1000 mg IV infusion at Day 1 and Weeks 2, 24, 26, and either Weeks 50 and 52 or Week 52 only

Control: Placebo

- Intercurrent events: Early study withdrawal prior to Week 76 due to lack of efficacy.
 It will be handled using composite strategy. That is, the early study withdrawals due to lack of efficacy will be considered as events.
- Summary measure: Difference in proportions at Week 76

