Early study withdrawals due to reasons other than lack of efficacy will be considered as having missing data.

The missing UPCR and eGFR values will be imputed by the multiple imputation model specified for the primary endpoint in Section 4.2.2 using data from the patients who did not experience death, treatment failure or early study withdrawal due to lack of efficacy.

The death or renal related event endpoint for patients who withdrew early from the study for reasons other than lack of efficacy will then be evaluated based on only the following criteria using the imputed UPCR and eGFR values:

- Worsening proteinuria, defined as a confirmed ≥50% increase in UPCR to a value ≥3
- Worsening eGFR, define as a confirmed ≥30% decrease in eGFR to a value <60

The death or treatment failure will not be imputed.

Worsening proteinuria will be assessed based on 24-hour UPCR which is collected at Week 24, 50 and 76 as per the protocol.

Imputation of eGFR will be made only for the Weeks 24, 36, 50, 64, and 76 as these visits are included in the imputation model (Section 4.2.2). If eGFR values worsened at other missing visits (Weeks 2, 4, 12, 26, and 52) that are not imputed, the worsening due to disease activity should be captured at the next observed or imputed visits. Study withdrawals who have not achieved the event following imputation of their UPCR or eGFR data will be assumed to have not had the event.

The multiple imputation parameters, analysis and pooling steps will be similar to the methods specified in the Section 4.2.2.

4.3.1.5 Mean Change in eGFR from Baseline to Week 76

Change in eGFR from baseline at Week 76 will be analyzed using Analysis of Covariance (ANCOVA) model. The response variable in the model will be change in eGFR from baseline at Week 76. Treatment group (combined obinutuzumab vs. placebo), baseline eGFR and the stratification factors race and region will be included in the model as independent variables. The adjusted difference between the treatment group with 95% CI and p-value will be presented.

The eGFR values for patients who died will be imputed with 0 (composite strategy). All other intercurrent events (specified in Section 4.3) will be handled using treatment policy strategy.

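### After Week 76 a composite rule written for response endpoints also governs the harm endpoint of death or renal-related events, so unrelated withdrawals and open-label entry could be scored as events, unlike the Week 76 rule

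*SAP*

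**What the plan says.** **After Week 76 (SAP 4.6.6).** One estimand serves as a default: "The estimand attributes for the binary endpoints are defined as follows unless otherwise specified". Its variable is "Endpoint (variable): The primary and key secondary endpoints at Week 106, 132" and the later visits to Week 210, so it includes the key secondary endpoint of death or renal-related events. On intercurrent events it says: "Rescue therapy, treatment failure, death, early study withdrawal and entering into the OLT will be handled using a composite strategy". No reason for withdrawal is distinguished. Treatment discontinuation follows treatment policy, and entry into study follow-up (SFU) follows a hypothetical strategy. The one sentence specific to this endpoint says that "death or renal-related events through the post-Week 76 visits will be evaluated from the beginning of the study". That sets the counting window and nothing else.

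**Through Week 76 (SAP 4.3.1.4).** The same endpoint has its own estimand. The components are death, treatment failure, confirmed proteinuria worsening and confirmed eGFR worsening. The estimand lists "Intercurrent events: Early study withdrawal prior to Week 76 due to lack of efficacy" and adds: "That is, the early study withdrawals due to lack of efficacy will be considered as events". For the rest, "Early study withdrawals due to reasons other than lack of efficacy will be considered as having missing data", and their UPCR and eGFR values are multiply imputed.

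**General binary rule (SAP 4.3).** Patients with a composite intercurrent event are called non-responders. That is clear for a response endpoint. For an endpoint where the event is the bad outcome, it does not say whether the patient is coded as having the event.

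**The concern.** The sponsor has already recognised that the general binary rule does not suit this endpoint. Section 4.3.1.4 replaces it, and the SAP's amendment rationale attributes that change to health authority feedback. Section 4.6.6, listed in the same rationale as newly added, does not carry the replacement over.

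Take a patient with stable kidney function who leaves the study at Week 100 because of a move. Under the 4.3.1.4 principle that patient has missing data. Under the literal 4.6.6 default the patient has a death or renal-related event at Week 106.

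Two things are at stake. The label would no longer describe what is counted, and the arm difference would partly reflect unrelated withdrawal. The choice could also be made late: under protocol Section 3.1.5 the sponsor is unblinded after the primary analysis while blinded follow-up continues, so coding left open now may be settled by people who know the assignments.

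**Working it through.** The documents give no post-Week 76 figure for this endpoint, so there is no stated result to reproduce. The check sets the rules side by side and then illustrates the gap with assumed rates.

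**Rules compared**

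| Situation | 4.3.1.4 (through Week 76) | 4.6.6 default, read literally |
|---|---|---|
| Withdrawal, lack of efficacy | event | composite (event) |
| Withdrawal, other reason | missing data | composite (event) |
| OLT entry | does not arise; OLT starts at Week 80 or later | composite (event) |
| Corticosteroid-only rescue | not an event (outside treatment failure) | unclear |
| SFU entry | does not arise | hypothetical strategy, not an event |

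**Illustration.** Let e be the proportion with a component event, w the proportion withdrawing, f the share of withdrawals that are for lack of efficacy, and s the proportion with corticosteroid-only rescue. All are assumed and treated as independent; OLT entry is left out.

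- 4.3.1.4 rule: 1 − (1 − e)(1 − wf)
- 4.6.6 literal rule: 1 − (1 − e)(1 − w)(1 − s)

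With e = 10%, w = 10% and s = 0, the 4.6.6 rule gives 1 − 0.90 × 0.90 = 19.0%.

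| f | 4.3.1.4 rule | 4.6.6 literal | Excess (points) |
|---|---|---|---|
| 0 | 1 − 0.90 × 1.00 = 10.0% | 19.0% | 9.0 |
| 0.5 | 1 − 0.90 × 0.95 = 14.5% | 19.0% | 4.5 |
| 1 | 1 − 0.90 × 0.90 = 19.0% | 19.0% | 0 |

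Over e = 5–20%, w = 5–15% and f = 0–1, the excess from withdrawal alone runs from 0 to 14.25 points. The maximum is at e = 5%, w = 15%, f = 0: (1 − 0.95 × 0.85) − 0.05 = 0.1925 − 0.05. If corticosteroid-only rescue at s = 5% were also counted, that maximum becomes (1 − 0.95 × 0.85 × 0.95) − 0.05 = 18.3 points.

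**If composite meant no event.** Suppose withdrawal adds nothing and component events already recorded are kept. With the same inputs the proportion is e = 10.0%, against 10.0% to 19.0% under 4.3.1.4. The error is then 0 to 9.0 points downward.

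**Arm difference.** Assume true event proportions of 20% on placebo and 10% on obinutuzumab (difference −10.0 points), with f = 0 and s = 0.

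| Withdrawal, placebo / obinutuzumab | Placebo | Obinutuzumab | Difference (points) |
|---|---|---|---|
| 10% / 10% | 1 − 0.80 × 0.90 = 28.0% | 1 − 0.90 × 0.90 = 19.0% | −9.0 |
| 15% / 5% | 1 − 0.80 × 0.85 = 32.0% | 1 − 0.90 × 0.95 = 14.5% | −17.5 |
| 5% / 15% | 1 − 0.80 × 0.95 = 24.0% | 1 − 0.90 × 0.85 = 23.5% | −0.5 |

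The same true effect can look larger or almost vanish, depending on which arm has more unrelated withdrawal.

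**The case against.** Several parts of the opposing case stand.

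- **Direction.** Section 4.6.6 names a composite strategy but gives no coded value for a harm endpoint. Death and treatment failure are components in their own right, so coding withdrawal as no event would not erase a death. Inflation is the natural literal reading, not an established fact.
- **Corticosteroid-only rescue.** A reader might infer that every such course becomes a renal event, because Section 4.2.1.1 makes it one of two rescue categories. But that section extends the 12-week corticosteroid rule to response endpoints after Week 76, naming CRR, PRR, ORR and proteinuric response. Death or renal-related events is not named, and treatment failure leaves out corticosteroid-only rescue. The more specific text points against counting it, so this is a secondary ambiguity.
- **Fewer patients affected.** Those who stop blinded infusions without entering OLT go to SFU, which is not composite. What remains is true study withdrawal for other reasons, plus OLT entry.
- **Comparability.** A reader might blame this rule for making the later figures unreadable beside Week 76. That comparison is already limited: the later set contains only adequate responders who continued blinded treatment, missing data use last observation carried forward (LOCF), and the investigator-judged worsening criterion was not evaluated after Week 76.
- **Weight.** The SAP calls the analysis supportive and exploratory, and it lies outside the testing hierarchy.

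None of this supplies the missing rule for withdrawals unrelated to efficacy or for OLT entry.

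**Conclusion.** The gap is real but narrow. Followed literally, 4.6.6 scores withdrawals for any reason and OLT entry as death or renal-related events, while 4.3.1.4 scores only lack-of-efficacy withdrawals and treats the others as missing.

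It would be wrong to conclude that the Week 76 rule leaves out withdrawal altogether, since lack-of-efficacy withdrawals are events there. It would also be wrong to quote a fixed inflation factor. The size rests wholly on assumed rates. In the illustration it is 0 to 14.25 points from withdrawal alone, and it is zero if every withdrawal is for lack of efficacy and neither OLT entry nor corticosteroid-only rescue adds anyone. The bias in the arm difference can go either way. No confirmatory result is affected; the reason to act is that the repair is cheap and is best made before post-Week 76 data are read unblinded.

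**What to change.** Add an endpoint-specific estimand to SAP 4.6.6, for example:

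> *For death or renal-related events, the event definition and intercurrent-event handling of Section 4.3.1.4 apply, extended to the assessment visit. Events are death, treatment failure, confirmed UPCR or eGFR worsening, and study withdrawal due to lack of efficacy. Withdrawals for other reasons are missing data, handled by the LOCF rule of this section. Corticosteroid-only rescue is not in itself an event.*

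The LOCF reference is needed because the 4.3.1.4 imputation model stops at Week 76.

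State separately whether OLT entry for loss of response is an added event. It is not in the 4.3.1.4 definition, so if it is added, report the proportion with and without it.

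The cost is SAP wording and the matching programming. It needs reasons for study withdrawal, which the protocol already asks sites to document, and no new data.

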- Intercurrent events: Rescue therapy, treatment failure, study treatment discontinuation, or death prior to endpoint assessment. Rescue therapy, treatment failure and study treatment discontinuation will be handled using treatment policy strategy.
 - Death will be handled using composite strategy. Data after death will be imputed by a pre-specified single fixed value specified in the next sections for each of the continuous endpoints.
- Summary measure: Difference in adjusted means at a specified visit of interest

The intercurrent events are described in Section 4.2.1.1.

4.3.1 Key Secondary Endpoints

4.3.1.1 Proportion of Patients who Achieve a Proteinuric Response at Week 76

The proportion of patients who achieve a proteinuric response at Week 76 will be analyzed using a CMH test with region and race as stratification factors. Proteinuric response is defined as achievement of all of the following:

- UPCR < 0.8
- No occurrence of the following intercurrent events:
 - Rescue therapy, treatment failure, death, or early study withdrawal

Missing data: Data obtained from the central laboratory only will be used. UPCR will be imputed by multiple imputations using the model specified in Section 4.2.2. The same imputed datasets produced during the analysis of CRR will be used for the analysis of proteinuric response. The analysis will follow the same methods described in Section 4.2.2.

4.3.1.2 Proportion of Patients who Achieve CRR with Successful Prednisone Taper at Week 76

The proportion of patients who achieve CRR with successful prednisone taper at Week 76 is defined as achievement of CRR (defined as Section 4.2.1) at Week 76 with the following:

 No receipt of prednisone >7.5 mg/day (or equivalent) from Week 64 through Week 76

The endpoint will be analyzed using a CMH test with region and race as stratification factors.

Only oral corticosteroid will be considered for evaluating the no receipt of prednisone >7.5 mg/day (or equivalent) criteria and converted to prednisone equivalent dose when applicable.

Data Handling for Oral Corticosteroids

The study team will monitor oral corticosteroids on an ongoing basis for data quality and to ensure all dose adjustments are being correctly captured. All efforts will be made to resolve missing or ambiguous data prior to database lock. In the case that data queries cannot be resolved, data will be handled in a conservative manner as described in the sections below.

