Missing data will be imputed by multiple imputations using FCS predicted mean matching method. A set of candidate donors with 5 members is chosen for the predictive mean matching method. Only patients who did not experience death will be included in the imputation model. Separate imputation models will be used for each treatment group.

The models will contain the following variables (in order of being imputed):

- Baseline eGFR
- Log-serum Albumin at Baseline
- Region (stratification factor)
- Race (stratification factor)
- Sex
- Age
- BMI
- Week 24 eGFR
- Week 36 eGFR
- Week 50 eGFR
- Week 64 eGFR
- Log-serum Albumin at Week 76
- Week 76 eGFR

The imputation will be implemented using the following three standard steps to generate inference from the imputed data. The number of imputations will be set of 100.

1. Imputation step:

- The missing data will be imputed 100 times to generate 100 imputed datasets for the patients who did not experience death.
- Patients who experienced death will be added in each of the datasets to obtain full datasets including all the patients in the analysis population.
- A number of burn-in iterations of 100 and a seed of 5678234 will be used.
- Analysis step: Each of the 100 imputed datasets will be analyzed using ANCOVA model
- 3. **Pooling step:** The results from the 100 imputed datasets will be combined for inference following the methodology developed by Rubin (Rubin 1987).

4.3.1.6 Change in FACIT-F scale from Baseline to Week 76

Change in FACIT-F scale from baseline at Week 76 will be analyzed using ANCOVA model. The response variable in the model will be change in FACIT-F scale from baseline at Week 76. Treatment group, baseline FACIT-F scale and the stratification factors race and region will be included in the model as independent variables. The adjusted difference between the treatment group with 95% CI and p-value will be presented.

The FACIT-F scale for patients who died will be imputed with 0 (composite strategy). All other intercurrent events (specified in Section 4.3) will be handled using treatment policy strategy.

Missing data will be imputed by multiple imputations. Only patients who did not experience death will be included in the imputation model. Multiple imputation methods will be the same as described in Section 4.3.1.5.

The multiple imputation models will contain the following variables (in order of being imputed):

- Baseline FACIT-F score
- Region (stratification factor)

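### After Week 76 the SAP compares change in eGFR and FACIT-F as raw mean differences, dropping the baseline adjustment it specifies for the same variables at Week 76

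*SAP*

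**What the plan says.** **At Week 76.** SAP 4.3 defines the estimand for the continuous secondary endpoints with "Summary measure: Difference in adjusted means at a specified visit of interest". For eGFR (4.3.1.5): "Treatment group (combined obinutuzumab vs. placebo), baseline eGFR and the stratification factors race and region will be included in the model as independent variables". For FACIT-F (4.3.1.6): "Treatment group, baseline FACIT-F scale and the stratification factors race and region will be included in the model as independent variables". The analysis set is every randomised patient (SAP 3.1.2).

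**At Weeks 106, 132, 158, 184 and 210.** SAP 4.6.6 says of the same two variables: "The change from baseline for eGFR and FACIT-F post Week 76 will be summarized using descriptive statistics", and "A 95% CI of mean difference between the treatment groups will be presented". The estimand line reads "Summary measure: Difference in means at a specified visit of interest". No model, covariate or stratification factor is named. The analysis set is patients whom the investigator judged adequate responders at Week 76 and who continued blinded infusions.

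The same section calls the work supportive and exploratory. It lists two limitations: small numbers and "potential baseline imbalances between groups".

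The general considerations in SAP Section 4 stratify primary and secondary analyses by race and region by default. That default does not supply adjustment for the baseline value.

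**The concern.** The adjustment is present where randomisation protects the comparison and absent where it no longer does. One criterion for staying in the post-Week 76 set is an eGFR of at least 85% of baseline, which involves the baseline value itself. The sample-size section assumes CRR rates of 30% and 50%, so the two arms may well be filtered differently.

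A raw change score carries any baseline difference into the between-arm contrast through regression to the mean. Its interval is also wider than that of a baseline-adjusted estimate. Protocol 3.1.5 delays unblinding of investigators and patients in order to collect controlled data beyond Week 76, so readers are likely to take these intervals as evidence on longer-term kidney function and fatigue. Baseline eGFR and FACIT-F are already collected, and the model is already written.

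**Working it through.** **1. The plan's own figures.** The documents give no SD, correlation, sample size or power for this analysis. The only power figure is for CRR. With 126 per arm, 30% vs 50% and two-sided 5%, power = Φ[(0.20√126 − 1.96√(2×0.4×0.6)) / √(0.21+0.25)] = Φ(1.31) = 90.5%, which agrees with the stated 90% or so. It is used here only for the responder counts in step 4.

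**2. Shift from a baseline imbalance.** Let D be the baseline difference (obinutuzumab minus placebo) and b the slope of follow-up on baseline. The expected raw change contrast is the treatment effect plus (b − 1) × D. With equal SDs at baseline and follow-up, b = rho. ANCOVA removes the term if its linear model holds.

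**3. Interval width.** Var(change) = 2σ²(1 − rho) and Var(ANCOVA residual) = σ²(1 − rho²). The variance ratio, ANCOVA to raw, is (1 + rho)/2.

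Both rho and D below are assumed.

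| rho | Shift, D = 5 mL/min/1.73 m² | Shift, D = 3 FACIT-F points | SE ratio √((1+rho)/2) | ANCOVA CI narrower by about |
|---|---|---|---|---|
| 0.5 | −2.5 | −1.5 | 0.866 | 13% |
| 0.7 | −1.5 | −0.9 | 0.922 | 8% |
| 0.8 | −1.0 | −0.6 | 0.949 | 5% |
| 0.9 | −0.5 | −0.3 | 0.975 | 3% |

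A positive D pulls the raw contrast down, and a negative D pushes it up.

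**4. How large chance imbalance could be.** Suppose only the planned CRR responders continued: 126 × 0.50 = 63 and 126 × 0.30 ≈ 38. The SE of the baseline difference is then √(1/63 + 1/38) = 0.205 SD, with a 95% range of about ±0.40 SD. This is an illustration. Adequate response is broader than CRR, so more patients may continue, while later visits will have fewer.

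**5. Does adjustment deal with selection?** Three simulated settings, all with no treatment effect on the later eGFR, assumed baseline mean 100 and SD 30:

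- Selection related to baseline eGFR in the placebo arm only. D was about −8.3. The raw contrast was +3.4 (rho 0.6) or +1.6 (rho 0.8), and ANCOVA was about 0.
- The 85% rule plus a UPCR response of 75% vs 50%, correlated 0.2 to 0.4 with baseline eGFR. The baseline imbalance was 2.2 to 4.5. The raw contrast was roughly +0.4 to +1.4, and ANCOVA was within 0.1 of zero. With no such correlation, both were near zero.
- The 85% rule alone, with a Week 76 effect of 5 and no later effect. At baseline-to-Week 76 correlation 0.7, D was about 0.5, the raw contrast about −1.1 and ANCOVA about −1.0. At 0.85, D was about 0 and both were about −0.8.

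In the first two settings ANCOVA removes the error, because selection works through baseline. In the third it removes very little, because selection works through the Week 76 value.

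**The case against.** **Status.** The comparison is labelled exploratory, has no p-value and lies outside the testing sequence in SAP 2.1.1. The post-Week 76 exploratory endpoints listed in protocol 2.1.3 and SAP 1.1.1.3 are CRR, proteinuric response and ORR; change in eGFR and FACIT-F enters only through 4.6.6. The binary endpoints there are also reported simply, with no CMH test named. A plainer method for a descriptive extension can therefore be deliberate. This stands, and it limits the weight of the point. It does not fully answer it, because a between-arm difference with a 95% CI under a stated estimand is more than a table of means by arm.

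**Chance imbalance.** The raw interval already reflects chance imbalance. For that component, the shift and the extra width in the table are two views of one loss and should not be added. This stands.

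**Assumptions.** Once groups are no longer randomised, change scores and ANCOVA rest on different untestable assumptions, and neither is automatically unbiased. The third simulated setting shows this. It stands, and it rules out presenting ANCOVA as a cure.

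**Stronger readings.** A reader might infer that the SAP expects imbalance, or that the reported estimates are biased. The documents support neither: the SAP calls the imbalance potential, and nothing shows that one exists, in which direction, or how large it is.

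**Conclusion.** The inconsistency is plain in the text. The same two variables go from a difference in adjusted means at Week 76 to an unadjusted difference afterwards, in a response-selected subset, without a stated reason.

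The consequence is conditional and modest. The raw contrast moves by (rho − 1) × D relative to ANCOVA, and the interval gain runs from about 13% at rho 0.5 down to about 3% at rho 0.9. These figures assume equal SDs and a linear relation with baseline, and take rho and D from outside the documents. If the arms turn out balanced and rho is high, little changes.

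One might also infer that adjustment would turn these contrasts into unbiased estimates of the long-term effect. It would not: it corrects measured baseline differences and leaves bias from selection on Week 76 response. Nothing here touches the primary analysis, the key secondary tests or type I error control.

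**What to change.** In SAP 4.6.6:

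- Add at each visit an ANCOVA-adjusted difference with 95% CI for change in eGFR and change in FACIT-F, with treatment and the baseline value as terms.
- Include region and race as main effects where numbers allow, with a rule fixed in advance for collapsing or dropping them when levels are sparse. Without such a rule the choice becomes discretionary in small samples.
- Keep the raw means by arm as the descriptive table. The LOCF and death rules in 4.6.6 can stay as they are.
- State that adjustment does not restore the randomised comparison or remove bias from selection on Week 76 response. A table of baseline characteristics of the continuing patients by arm would let readers judge the imbalance.

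The cost is a few SAP sentences and reuse of the ANCOVA step already planned for Week 76. The baseline term uses one degree of freedom. Region (three levels) and race (two levels) as main effects use 2 + 1 = 3 more. The wording should be settled before the Sponsor is unblinded after the primary analysis (protocol 3.1.5).
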